12.6.3 Laboratory Data

All laboratory data will be summarized in International System (SI) units. The conversion factors from conventional to SI units will be documented in the Local Lab Conventions document for this study. In general, laboratory data will be presented by visit. Values at unscheduled visits will be included in the summary of maximum for all cycles and minimum for all cycles, which will present the largest and smallest values observed for each patient post-baseline for each test.

Selected parameters will be presented in shift tables of baseline against worst grade test result. The shift from baseline to worst post baseline (including unscheduled visit) NCI CTCAE Version 4.03 grade will be presented by dosing group and overall for albumin (albumin increased), AST (AST increased), ALT (ALT increased), bilirubin (bilirubin increased), creatinine (creatinine increased), hemoglobin (anemia), neutrophils (neutrophil count decreased), platelets (platelet count decreased), sodium (hyponatremia and hypernatremia), potassium (hypokalemia and hyperkalemia), calcium (hypocalcemia and hypercalcemia), phosphate (hypophosphatemia), and uric acid (hyperuricemia).

For sodium, potassium, and calcium, separate grading criteria exist depending whether the analyte is high or low. For the purpose of shift tables, all low values will be included in the Grade 0 group in the shift tables for high values, and vice versa (all high values should be included in the Grade 0 group in the shift tables for low values).

Subjects with at least 1 on-study measurement for each laboratory parameter will be included, regardless of whether or not a baseline assessment is present.

Clinical laboratory results will be listed by subject. Laboratory values that meet Grade 3 or 4 criteria according to NCI CTCAE Version 4.03 will also be listed separately.

Sponsor: Mirati Therapeutics, Inc.

Protocol no: 0103-020

12.6.4 Hematology

Hematology parameters include hemoglobin, platelet count, white blood cell (WBC) count, lymphocytes, monocytes, neutrophils, eosinophils, and basophils. The coagulation parameters include prothrombin time (PT), partial thromboplastin time (PTT) and international normalization ratio (INR).

Descriptive statistics will be provided for each test result and for change from baseline by cycle. Multiple measurements taken during the visit for a patient will be represented by the most severe value for each hematology test. The most severe value will be determined first by the value closest to the upper or lower limit of the normal limits (dependent on which direction is considered severe) if the value is within the normal limits. If the value is outside the normal limits, the value furthest from the upper or lower limit will be selected (dependent on which direction is considered severe). In the event that this algorithm does not allow for determining the most severe (e.g., a tie, etc.) the first chronological value will be selected. Low values are considered the most severe for all hematology parameters. Shift tables (for hemoglobin (anemia), neutrophils (neutrophil count decreased), platelets (platelet count decreased)), summarizing the shift from baseline grade to each post-baseline visit, maximum post-baseline CTCAE grade including unscheduled visits, and last assessment on study will be presented. Patients who develop a \geq Grade 3 toxicity will be listed.

12.6.5 Chemistry

Serum chemistry parameters include ALT, AST, alkaline phosphatase, lactate dehydrogenase (LDH), total bilirubin, direct bilirubin, indirect bilirubin, gamma glutamyl transferase (GGT), lipase, amylase, creatinine, uric acid, blood urea nitrogen (BUN), total protein, glucose (non-fasted), albumin, sodium, potassium, chloride, total calcium, magnesium, and bicarbonate.

Descriptive statistics will be provided for each test result and for change from baseline by cycle. Multiple measurements taken during the visit for a patient will be represented by the most severe value as noted in [Section 12.6.3](#). For all chemistry analytes, the most severe value is the highest value, with the exception of albumin, chloride, and bicarbonate. The most severe could be in either direction for glucose, potassium, sodium, and calcium. For these analytes, if within the normal limits, then the value closest to the normal limit (either direction) will be selected. If outside the normal limits, then the value most distant from the normal limit (either direction) will be used. Shift tables (for AST (AST increased), ALT (ALT increased), creatinine (creatinine increased), sodium (hyponatremia and hypernatremia), potassium (hypokalemia and hyperkalemia), calcium (hypocalcemia and hypercalcemia), phosphate (hypophosphatemia), and uric acid (hyperuricemia), summarizing the shift from baseline grade to each post-baseline visit, maximum post-baseline CTCAE grade including unscheduled visits, and last assessment on study will be presented. Patients who develop a \geq Grade 3 toxicity will be listed.

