## Cardiac Arrhythmias

Grade 3 AEs of QTc prolongation (> 500 msec) were reported in 4 of 435 patients in clinical trials with mocetinostat; 3 of those 4 events were also reported as part of SAEs. Three of the 4 patients already had a prolonged QTc at baseline. Three of the events of QTc prolongation occurred in a setting of GI disturbances associated with dehydration and/or hypotension. In 2 cases, there was definite hypokalemia, with concomitant low magnesium in one patient, and in both cases, the QTc values decreased quickly to baseline levels after IV administration of potassium and magnesium. Concomitant treatment with drugs identified as having the potential to cause QTc prolongation may have been a factor in 2 patients.

Although therapy with mocetinostat does not appear to be an obvious risk factor for development of QTc prolongation, ECG monitoring may be warranted in the settings of GI disturbances associated with dehydration and/or electrolyte abnormalities.

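### The SAP laboratory rules take the highest magnesium value as worst and give magnesium no shift table; the albumin, phosphate and coagulation rules also need correcting, with effects confined to by-visit summaries and shift tables

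*SAP*

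**What the plan says.** **Chemistry (SAP 12.6.5).** The section lists magnesium among the chemistry parameters: "sodium, potassium, chloride, total calcium, magnesium, and bicarbonate". For repeat results it says "Multiple measurements taken during the visit for a patient will be represented by the most severe value as noted in" Section 12.6.3. The direction follows: "For all chemistry analytes, the most severe value is the highest value, with the exception of albumin, chloride, and bicarbonate". Next comes a second group: "The most severe could be in either direction for glucose, potassium, sodium, and calcium".

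**Hematology and coagulation (SAP 12.6.4).** This section contains the actual selection algorithm and the sentence "Low values are considered the most severe for all hematology parameters". It also says "The coagulation parameters include prothrombin time (PT), partial thromboplastin time (PTT) and international normalization ratio (INR"), but gives these tests no direction.

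**Shift tables.** SAP 12.6.3 lists the analytes to be shifted from baseline to worst grade, among them "albumin (albumin increased") and phosphate. SAP 12.6.5 gives its own shift list, which includes phosphate but not albumin or bilirubin. Magnesium is in neither list.

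**Grading and collection.** SAP 12.6.8 grades both magnesium and phosphate. SAP Table 3 and Protocol Table 13 include magnesium but not phosphate.

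**Clinical background.** Protocol 1.2.3, under Cardiac Arrhythmias, describes two earlier QTc prolongation cases with definite hypokalemia, "with concomitant low magnesium in one patient".

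**The concern.** A worst-value rule exists so that a table shows the clinically adverse end of a set of repeat results. If the rule points the other way, a low result and a corrected repeat in the same visit are represented by the corrected one.

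For magnesium the low end matters in this program. The protocol reports low magnesium alongside hypokalemia in one QTc case. It also reports treatment-related diarrhea in 46.7% and vomiting in 37.3% of patients on single-agent mocetinostat, and advises ECG attention when gastrointestinal disturbance brings electrolyte abnormalities. Potassium, the companion electrolyte, is handled in both directions and has low and high shift tables. Magnesium has neither.

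The other items are of the same kind: a shift label that contradicts the direction used elsewhere for the same analyte, a planned table with no scheduled data, and a group of tests with no stated direction. Each leaves the programmer to guess, or to follow text that gives the wrong summary.

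**Working it through.** The plan states no figure on this point, so the check compares its lists and then applies the written rule to assumed values.

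**1. Direction of each collected chemistry analyte.** SAP Table 3 and Protocol Table 13 each list 20 chemistry analytes, counting bilirubin once. SAP 12.6.5 names 3 exceptions and 4 two-directional analytes. That leaves 20 − 3 − 4 = 13 under highest-is-worst: ALT, AST, alkaline phosphatase, LDH, bilirubin, GGT, lipase, amylase, creatinine, BUN, uric acid, total protein and magnesium.

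**2. Grading against shift tables.** SAP 12.6.8 grades 12 chemistry analytes. Two of them, magnesium and alkaline phosphatase, appear in no shift list.

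**3. Planned outputs against collection.** Phosphate is the only analyte with a planned shift table that is in neither laboratory panel. It is also the only graded chemistry analyte not collected.

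**4. The two shift lists.** Albumin and bilirubin are in the 12.6.3 list and missing from the 12.6.5 list. For albumin, 12.6.3 labels the shift as an increase. In 12.6.5 albumin is exempt from highest-is-worst, which implies that low is worst.

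**5. The within-visit rule applied.** These pairs are assumed illustrations, not trial data.

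| Test | Two results in one visit | Kept by the written rule | Kept if the adverse direction is used |
|---|---|---|---|
| Magnesium, mmol/L | 0.45, 0.80 | 0.80 | 0.45 |
| Magnesium, mmol/L | 0.60, 0.72 | 0.72 | 0.60 |
| Magnesium, mmol/L | 0.66, 0.69 | 0.69 | 0.66 |
| INR | 1.1, 3.0 | 1.1, only if the low rule is read to cover coagulation | 3.0 |
| INR | 1.3, 2.0 | 1.3, only if the low rule is read to cover coagulation | 2.0 |

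With one result per visit nothing changes.

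**6. Coagulation.** SAP 12.6.4 names hematology and coagulation parameters in separate sentences, and Table 3 shows them as separate panels. The low-is-worst sentence speaks of hematology parameters. On that reading coagulation has no direction. On the looser reading it inherits low, which is the wrong end for detecting prolonged clotting. Either way the text needs a sentence.

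**7. Cross-reference.** SAP 12.6.5 sends the reader to 12.6.3 for the selection algorithm, but the algorithm is in 12.6.4.

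**The case against.** The strongest reply is that extreme values are still visible, and most of it stands.

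- SAP 12.6.3 summarizes each patient's post-baseline minimum and maximum for every test, unscheduled visits included. Low magnesium sets the minimum; prolonged clotting sets the maximum.
- Grade 3 or 4 values are listed separately, which covers magnesium, and all results are listed by patient.
- Protocol 8.2.1 makes an abnormal result that needs treatment an adverse event, so a treated low magnesium should reach the adverse event tables.
- SAP Appendix 4 generally keeps unscheduled values out of post-baseline tabulations. A recheck at an unscheduled visit would not displace the scheduled low value; only a repeat assigned to the same visit triggers the rule.
- After screening, coagulation is tested only as clinically indicated (Protocol Table 1), so repeats within a visit should be few.
- Both documents promise shift tables for selected parameters only, and SAP 4.0 foresees a final version before database lock.

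A reader might therefore infer too much in four ways. That low magnesium or prolonged clotting is hidden is not supported, given the outputs above. That the rule for coagulation is plainly reversed is not supported, because the low rule is written for hematology. That albumin's worst-value rule is wrong is not supported; only its shift label conflicts, and whether the label would change any output depends on CTCAE text that the documents do not reproduce. That the QTc experience measures the impact is not supported either: low magnesium was a concomitant finding in one patient, and the same protocol section does not regard mocetinostat as an obvious risk factor for QTc prolongation.

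The safeguards do not make the corrections unnecessary. Listings are not summaries, and the minimum summary reports values rather than grades. Grade 1 or 2 low magnesium thus has no planned grade-based laboratory table. No coagulation test is on the graded list, so prolonged clotting may not reach the Grade 3/4 listing.

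**Conclusion.** The point holds as a minor correction to stated analysis rules. Low magnesium is understated in by-visit summaries when a visit has more than one result, and magnesium is absent from the shift tables. The albumin shift label conflicts with 12.6.5, the phosphate tables have no collected source in either document, and coagulation lacks a direction.

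The effect is limited to by-visit summaries and shift tables. No efficacy endpoint, sample size or patient procedure is affected. Its frequency cannot be calculated, because the documents do not say how often a visit yields repeat results. The missing magnesium shift table, the albumin label and the phosphate tables do not depend on repeats. The phosphate conclusion assumes that the two laboratory panels are the complete list of what is collected.

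**What to change.** In the SAP:

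1. Add magnesium to the two-directional analytes in 12.6.5, and add low and high magnesium shifts to the shift lists.
2. Change the albumin shift in 12.6.3 to the low direction, and align the 12.6.3 and 12.6.5 lists (albumin and bilirubin are missing from the latter).
3. Delete phosphate from the shift and grading lists, or confirm where the data come from.
4. State in 12.6.4 that high is worst for PT, PTT and INR.
5. Point the 12.6.5 cross-reference to 12.6.4 instead of 12.6.3.

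The cost is SAP wording and minor programming. The changes can go into the final SAP version planned before database lock.

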12.6.6 Urinalysis

Urinalysis results for the parameters blood, protein, and glucose will be listed.

12.6.7 Thyroid

Results will be listed for thyroid-stimulating hormone (TSH), and if TSH is abnormal, then Free-T3 and Free-T4 will also be listed.

12.6.8 CTCAE Coding of Laboratory Data

Where laboratory values are categorized into NCI CTCAE v4.03 grades, the categories are defined according to the criteria available on the following website:

<http://evs.nci.nih.gov/ftp1/CTCAE/About.html>

Sponsor: Mirati Therapeutics, Inc.

Protocol no: 0103-020

Note that grades are applied based only on the numeric SI value of the parameter assessed; clinical signs and symptoms are not considered. For example, Grade 4 hyperglycemia will be assigned based solely on the value of the glucose measurement, and acidosis will not be considered. Where categories are only distinguished by clinical signs or symptoms, the lowest of the possible grades will be assigned.

NCI CTCAE grades will be applied for the following lab parameters:

- Hematology: hemoglobin, white blood cell (WBC), lymphocyte, neutrophils, and platelets.
- Chemistry: ALT, albumin, Alkaline, phosphatase, AST, total bilirubin, calcium, creatinine, phosphate, magnesium, potassium, sodium, uric acid.

Laboratory measurements that are within their institutional limits of normal and are not graded as 1-4, per the CTCAE, will be summarized as "Grade 0," which is defined as normal.

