#### **9.5.3 Clinical and Laboratory Assessments**

Clinical and laboratory assessments include clinical laboratory tests (hematology, coagulation, urinalysis, thyroid function tests and chemistry), vital signs, ECHO and 12-lead ECGs.

Clinical laboratory results will be listed by patient and, as appropriate, summarized descriptively, which will include a display of change from baseline. Selected parameters will be presented in shift tables of baseline against worst grade test result. Laboratory values outside of the normal ranges will be identified. Laboratory values that meet Grade 3 or 4 criteria according to NCI CTCAE v.4.03 will be listed and summarized.

ECG assessments will be evaluated for change of QTc from baseline as an exposure: response analysis. The investigator's interpretation of QTc will be used in the clinical management of patients. The study analysis will use the Fridericia formula applied programmatically to the ECG data collected in CRFs.

Vital signs, ECHO and ECG measurements will be listed for each patient at each visit. Descriptive statistics of observed values and changes from baseline will be summarized by treatment group.

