8.3 Safety Variables

Adverse events and laboratory values will be graded according to the National Cancer Institute (NCI) Common Terminology Criteria for Adverse Events (CTCAE) Version 4.03.

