8.3.1 Adverse Events

AEs will be coded using Medical Dictionary for Regulatory Activities (MedDRA, Version 15.1 or higher).

Baseline Signs and Symptoms

- Signs and symptoms of the patient's cancer diagnosis and/or comorbidities present on Day 1 of study drug dosing are recorded in the CRF as non-treatment emergent AEs, with actual start date, which will most often predate first dose. Baseline signs and symptoms will be reported separately from TEAEs.

Treatment-Emergent AEs (TEAEs)

- TEAEs are AEs that begin on Day 1 of study treatment or later during the on-study period. Baseline signs and symptoms that change attribution or severity during the on-study period are TEAEs. Any ongoing TEAEs that changes in attribution or severity is captured as a new AE.

Adverse Events of Special Interest (AESI)

AEs of special interest (AESI) for durvalumab based on observed safety event during durvalumab monotherapy and/or class effects for inhibitors of PD-L1 or PD-1 include:

- Colitis
- Pneumonitis
- Alanine aminotransferase (ALT)/aspartate aminotransferase (AST) increases / hepatitis / hepatotoxicity
- Neuropathy / neuromuscular toxicity (i.e., events of encephalitis, peripheral motor and sensory neuropathies, Guillain-Barré, and myasthenia gravis)
- Endocrinopathy (i.e., events of hypophysitis, adrenal insufficiency, and hyper- and hypothyroidism)
- Dermatitis
- Nephritis
- Pancreatitis (or labs suggestive of pancreatitis – increased serum lipase, increased serum amylase).

Immune-related Adverse Event (irAE)

An irAE is defined as an AE that is associated with drug exposure and is consistent with an immune-mediated mechanism of action and where there is no clear alternate aetiology.

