8.3.3 Clinical Laboratory Assessments

Clinical laboratory parameters to be collected routinely on-study are listed in Table 3 below.

Table 3: Laboratory Safety Parameters

Hematology Panel	Blood Chemistry Panel
Hemoglobin	Alanine aminotransferase (ALT)
Platelet count	Aspartate aminotransferase (AST)
White blood cell count (WBC)	Alkaline phosphatase
Neutrophil count	Lactate dehydrogenase (LDH)
Lymphocyte count	Total bilirubin (if Total bilirubin is $\geq 2 \times \text{ULN}$ and no evidence of Gilbert's syndrome, then fractionate into direct and indirect bilirubin)
Basophil count	Gamma glutamyltransferase Screening, Day 1, and as clinically indicated
Monocyte count	Lipase
Eosinophil count	Amylase
	Creatinine
Coagulation	Blood urea nitrogen (BUN) or urea, depending on local practice
International normalized ratio (INR)	Uric acid
Prothrombin time (PT)	Total protein
Partial thromboplastin time (PTT)	Glucose (non-fasted)
	Albumin
Urinalysis (dip stick)	Calcium
Blood	Sodium
Glucose	Potassium
Protein	Chloride
	Magnesium
Thyroid Function Test	Bicarbonate $[\text{CO}_2]$
Thyroid-stimulating hormone (TSH)	
Free-T3 (if TSH abnormal)	
Free-T4 (if TSH abnormal)	

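### The list of CTCAE-graded chemistry tests in SAP 12.6.8 omits lipase, amylase, glucose and GGT, so the promised Grade 3-4 laboratory output would be incomplete

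*SAP*

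**What the plan says.** SAP 12.6.8 states that CTCAE grades are applied to a named set of laboratory parameters. The wording is closed, with nothing to mark the tests as examples. The chemistry entry is "Chemistry: ALT, albumin, Alkaline, phosphatase, AST, total bilirubin, calcium, creatinine, phosphate, magnesium, potassium, sodium, uric acid". Just above it, the same section explains that grades rest on the numeric value alone and illustrates this with glucose: "Grade 4 hyperglycemia will be assigned based solely on the value of the glucose measurement".

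The collected panel is wider. SAP Table 3 (section 8.3.3) and Protocol Table 13 include lipase, amylase, non-fasted glucose and GGT. Table 3 gives the GGT timing as "Gamma glutamyltransferase Screening, Day 1, and as clinically indicated". SAP 12.6.5 carries all four into the chemistry analysis, for example "gamma glutamyl transferase (GGT), lipase, amylase, creatinine".

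The output commitments do not restrict the tests:

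- Protocol 9.5.3: "Laboratory values that meet Grade 3 or 4 criteria according to NCI CTCAE v.4.03 will be listed and summarized".
- SAP 12.6.3: "Laboratory values that meet Grade 3 or 4 criteria according to NCI CTCAE Version 4.03 will also be listed separately".
- SAP 12.6.5: chemistry patients who reach Grade 3 or higher are to be listed.
- SAP 8.3, in general terms: "Adverse events and laboratory values will be graded according to the National Cancer Institute (NCI) Common Terminology Criteria".

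**The concern.** A test that is never graded cannot appear in an output selected by grade. If the programmer follows 12.6.8, the Grade 3-4 laboratory listing and summary will contain no lipase, amylase, glucose or GGT value, however extreme. A reader would have no sign that these tests were left out and could take their absence as a clean result.

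This matters most for lipase and amylase. SAP 8.3.1 counts "increased serum lipase, increased serum amylase" as part of the pancreatitis event of special interest, and Protocol Table 9 makes asymptomatic amylase or lipase of Grade 3 or above a reason to hold study drug. Glucose is also relevant, since Protocol 1.3.3 lists type 1 diabetes mellitus among the durvalumab events of special interest.

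The programmed grade is also a check that does not depend on investigator action. Under Protocol 8.2.1 a laboratory abnormality is reported as an adverse event only if it meets one of the stated conditions, such as symptoms, further tests or a dosing change. A Grade 3 value that nobody acted on need not become an adverse event, and the laboratory grade would show it.

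**Working it through.** There is no planned figure to reproduce. The check compares the lists and then asks whether the documents treat the missing tests as gradable.

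**1. Collected panel.** SAP Table 3 has 20 chemistry entries: ALT, AST, alkaline phosphatase, LDH, total bilirubin, GGT, lipase, amylase, creatinine, BUN, uric acid, total protein, glucose, albumin, calcium, sodium, potassium, chloride, magnesium and bicarbonate. SAP 12.6.5 names 22, because it counts direct and indirect bilirubin separately (20 + 2 = 22).

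**2. Graded list.** SAP 12.6.8 names 12 chemistry tests, reading the split alkaline phosphatase entry as one.

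**3. Overlap.** Phosphate is graded but appears in neither Table 3 nor Protocol Table 13, so 12 − 1 = 11 graded tests are actually collected. The collected but ungraded entries number 20 − 11 = 9: LDH, GGT, lipase, amylase, BUN, total protein, glucose, chloride and bicarbonate.

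**4. Which of the nine do the documents show to have grades?**

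| Test | Evidence in the documents |
|---|---|
| Lipase, amylase | Protocol Table 9 sets a hold rule at Grade 3 and above |
| Glucose | SAP 12.6.8's own Grade 4 example; Protocol 1.3.3 reports hyperglycaemia among treatment-related events of Grade 3 or higher |
| GGT | Protocol 1.3.3 reports GGT increased among events of Grade 3 or higher, at 3.6% and 2.7% in two durvalumab monotherapy studies |

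These four are the clear omissions. The documents show no grades for the other five, so the point does not extend to them.

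**5. Effect of the omission.** Protocol 9.5.3, SAP 12.6.3 and SAP 12.6.5 select values or patients by CTCAE grade. With no grade assigned, the four tests contribute nothing. The shift tables in SAP 12.6.3 and 12.6.5 also leave them out, although they do include the uncollected phosphate.

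**6. Volume of ungraded results.** By the schedule of assessments (Table 1), serum chemistry is drawn on Days 1 and 15 of Cycles 1 to 3, which is 3 × 2 = 6 draws from Cycle 1 Day 1 to Cycle 3 Day 15. For lipase, amylase and glucose this gives 6 × 3 = 18 results per patient who reaches that visit, none with a programmed grade. GGT is scheduled only at screening and Cycle 1 Day 1, then as clinically indicated. The 18 counts all results, most of which may be normal. It is not an estimate of missed Grade 3-4 values.

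**7. After the correction.** Adding the four tests raises the collected and graded count from 11 to 15 of the 20 Table 3 entries.

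**The case against.** The best counter-argument is that little safety information is lost. If Table 9 is followed, a Grade 3 lipase or amylase leads to a hold and a work-up, and either makes it an adverse event under Protocol 8.2.1. The investigator then grades it, and it enters the tables of Grade 3 or higher events in SAP 12.6.1. Raw values are listed by patient, and all-cycle maxima and minima are summarised. Normal ranges are evidently available, because Protocol 9.5.3 says out-of-range values will be identified. All of this stands and limits the weight of the point. It leaves the value that was not acted on, and it leaves the reader to work out grades from raw results produced by local laboratories (Protocol 7.3.4).

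A second argument is that Protocol section 9 lets the SAP modify the protocol's analysis plans, so a narrower list is allowed. But the SAP repeats the unrestricted Grade 3-4 listing in 12.6.3 and 12.6.5 and gives no reason for narrowing it. The conflict is inside the SAP as well as with the protocol.

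Third, the table shells are in a separate document, and a final SAP is due before database lock. Either might resolve the matter in practice, but neither alters the rule now written in 12.6.8.

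Two smaller points are fair. SAP 8.3 mainly names the grading system, so it is weak evidence of a conflict. Lipase and amylase do not appear in Protocol 1.3.3's list of treatment-related events of Grade 3 or higher in the 970-patient monotherapy group, so frequent Grade 3 values should not be assumed.

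**Conclusion.** The point holds. Four collected chemistry tests, for which the documents themselves show CTCAE grades, are missing from the closed grading list. Applied literally, 12.6.8 leaves them out of the Grade 3-4 output that the protocol and two other SAP sections promise. The hyperglycemia example and the uncollected phosphate suggest that the list was not reconciled with this trial's panel.

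The size is modest. No primary endpoint or data collection is affected, and raw data and adverse event reporting give partial cover. The gap is a promised safety output that is incomplete for tests tied to an event of special interest and a hold rule. The conclusion assumes that programming follows 12.6.8 as written. The number of Grade 3-4 values that would be missed cannot be derived from the documents. The GGT rates above are adverse event rates on durvalumab alone, so they show relevance and do not give an expected count.

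**What to change.** In SAP 12.6.8, add lipase, amylase, GGT and glucose to the graded chemistry list. Grade glucose in both directions, since 12.6.5 already treats either extreme as potentially severe, and note that samples are non-fasted. State that all graded tests feed both the Grade 3-4 listing and the summary promised in Protocol 9.5.3. Confirm that phosphate is collected, or remove it from 12.6.8 and from the shift tables in 12.6.3 and 12.6.5.

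Adding lipase and amylase to the shift tables is optional, because Protocol 9.5.3 promises shift tables only for selected parameters.

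The cost is one edited list and a few rows in existing programs, with no new data. The final SAP due before database lock is a natural place for it. The one small drawback is that non-fasted glucose will produce some low-grade hyperglycemia counts.
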